15.70.2	Descriptive Statistics for Low Contrast Visual Acuity Score (Chart Type 1.25%) and Change From Baseline to Each Visit by Treatment Group	mITT2 Population	Part B
15.71.1	Exploratory Analysis: 12-Item Multiple Sclerosis Walking Scale Score Change From Baseline to Week 48	mITT2 Population	Part A

Summary number	Title	Population	Data Lock
15.71.2	Exploratory Analysis: 12-Item Multiple Sclerosis Walking Scale Score Change From Baseline to Each Visit	mITT2 Population	Part B
15.72.1	Descriptive Statistics for 12-Item Multiple Sclerosis Walking Scale Score and Change From Baseline to Each Visit by Treatment Group	mITT2 Population	Part A
15.72.2	Descriptive Statistics for 12-Item Multiple Sclerosis Walking Scale Score and Change From Baseline to Each Visit by Treatment Group	mITT2 Population	Part B
15.73.1	Distribution of Clinical Relapsing Patients by Treatment Group	ITT Population	Part A
15.73.2	Distribution of Clinical Relapsing Patients by Treatment Group	ITT Population	Part B
15.74.1	Distribution of Protocol Defined Relapsing Patients by Treatment Group	ITT Population	Part A
15.74.2	Distribution of Protocol Defined Relapsing Patients by Treatment Group	ITT Population	Part B
15.75.1	Descriptive Statistics For mRS at Week 72 by Treatment Group	mITT2 Population	Part A
15.75.2	Descriptive Statistics For mRS at Week 72 by Treatment Group	mITT2 Population	Part B
15.76.1	Distribution of mRS at Week 72 by Treatment Group	mITT2 Population	Part A
15.76.2	Distribution of mRS at Week 72 by Treatment Group	mITT2 Population	Part B
15.77.1	Exploratory Analysis: Time to 12 Weeks Confirmed Disability Progression as Measured by T25FW	ITT Population	Part A
15.77.2	Exploratory Analysis: Time to 12 Weeks Confirmed Disability Progression as Measured by T25FW	ITT Population	Part B
15.78.1	Exploratory Analysis: Proportional Hazards Assumption Evaluation: Time to 12 Weeks Confirmed Disability Progression as Measured by T25FW	ITT Population	Part A
15.78.2	Exploratory Analysis Proportional Hazards Assumption Evaluation: Time to 12 Weeks Confirmed Disability Progression as Measured by T25FW	ITT Population	Part B
15.79.1	Distribution of 12 Weeks Confirmed Disability Progression as Measured by T25FW by Treatment Group	ITT Population	Part A
15.79.2	Distribution of 12 Weeks Confirmed Disability Progression as Measured by T25FW by Treatment Group	ITT Population	Part B
15.80.1	Tolerability by Treatment Group	ITT Population	Part A
15.80.2	Tolerability by Treatment Group	ITT Population	Part B
15.81.1	Study Drug Exposure by Treatment Group	Safety Population	Part A
15.81.2	Study Drug Exposure by Treatment Group	Safety Population	Part B
15.82.1	Off-Drug Follow-Up Study Duration by Treatment Group	Safety Population	Part A
15.82.2	Off-Drug Follow-Up Study Duration by Treatment Group	Safety Population	Part B

Summary number	Title	Population	Data Lock
15.83.1	Adverse Events by System Organ Class, Preferred Term, and Treatment Group	Safety Population	Part A
15.83.2	Adverse Events by System Organ Class, Preferred Term, and Treatment Group	Safety Population	Part B
15.84.1	Adverse Events by System Organ Class, Preferred Term, Severity, and Treatment Group	Safety Population	Part A
15.84.2	Adverse Events by System Organ Class, Preferred Term, Severity, and Treatment Group	Safety Population	Part B
15.85.1	Treatment-Related Adverse Events by System Organ Class, Preferred Term, and Treatment Group	Safety Population	Part A
15.85.2	Treatment-Related Adverse Events by System Organ Class, Preferred Term, and Treatment Group	Safety Population	Part B
15.86.1	Treatment-Related Adverse Events by System Organ Class, Preferred Term, Severity, and Treatment Group	Safety Population	Part A
15.86.2	Treatment-Related Adverse Events by System Organ Class, Preferred Term, Severity, and Treatment Group	Safety Population	Part B
15.87.1	Serious Adverse Events by System Organ Class, Preferred Term, and Treatment Group	Safety Population	Part A
15.87.2	Serious Adverse Events by System Organ Class, Preferred Term, and Treatment Group	Safety Population	Part B
15.88.1	Adverse Events Causing Discontinuation of the Study Drug by System Organ Class, Preferred Term, and Treatment Group	Safety Population	Part A
15.88.2	Adverse Events Causing Discontinuation of the Study Drug by System Organ Class, Preferred Term, and Treatment Group	Safety Population	Part B
15.89.1	Non-Serious Adverse Events by System Organ Class, Preferred Term, and Treatment Group	Safety Population	Part A
15.89.2	Non-Serious Adverse Events by System Organ Class, Preferred Term, and Treatment Group	Safety Population	Part B
15.90.1	Adverse Events by System Organ Class, Preferred Term, Outcome, and Treatment Group	Safety Population	Part A
15.90.2	Adverse Events by System Organ Class, Preferred Term, Outcome, and Treatment Group	Safety Population	Part B
15.91.1	Adverse Events That Occurred After Study Drug Discontinuation by System Organ Class, Preferred Term, and Treatment Group	Safety Population	Part A
15.91.2	Adverse Events That Occurred After Study Drug Discontinuation by System Organ Class, Preferred Term, and Treatment Group	Safety Population	Part B
15.92.1	Serum Chemistry Laboratory Test Results and Changes From Baseline to Each Visit by Treatment Group	Safety Population	Part A
15.92.2	Serum Chemistry Laboratory Test Results and Changes From Baseline to Each Visit by Treatment Group	Safety Population	Part B

Summary number	Title	Population	Data Lock
15.93.1	Hematology Laboratory Test Results and Changes From Baseline to Each Visit by Treatment Group	Safety Population	Part A
15.93.2	Hematology Laboratory Test Results and Changes From Baseline to Each Visit and by Treatment Group	Safety Population	Part B
15.94.1	Serum Chemistry Laboratory Tests Shifts From Baseline to Each Visit by Treatment Group	Safety Population	Part A
15.94.2	Serum Chemistry Laboratory Tests Shifts From Baseline to Each Visit by Treatment Group	Safety Population	Part B
15.95.1	Hematology Laboratory Tests Shifts From Baseline to Each Visit and by Treatment Group	Safety Population	Part A
15.95.2	Hematology Laboratory Tests Shifts From Baseline to Each Visit and by Treatment Group	Safety Population	Part B
15.96.1	Serum Chemistry Laboratory Tests Abnormal Results by Treatment Group	Safety Population	Part A
15.96.2	Serum Chemistry Laboratory Tests Abnormal Results by Treatment Group	Safety Population	Part B
15.97.1	Hematology Laboratory Tests Abnormal Results by Treatment Group	Safety Population	Part A
15.97.2	Hematology Laboratory Tests Abnormal Results by Treatment Group	Safety Population	Part B
15.98.1	Serum Chemistry Laboratory Tests Potentially Clinically Significant Abnormal Results by Treatment Group	Safety Population	Part A
15.98.2	Serum Chemistry Laboratory Tests Potentially Clinically Significant Abnormal Results by Treatment Group	Safety Population	Part B
15.99.1	Hematology Laboratory Tests Potentially Clinically Significant Abnormal Results by Treatment Group	Safety Population	Part A
15.99.2	Hematology Laboratory Tests Potentially Clinically Significant Abnormal Results by Treatment Group	Safety Population	Part B
15.100.1	Shift Analysis for Serum Chemistry Laboratory Tests Abnormal Values From Baseline to Any Time During the Study by Treatment Group	Safety Population	Part A
15.100.2	Shift Analysis for Serum Chemistry Laboratory Tests Abnormal Values From Baseline to Any Time During the Study by Treatment Group	Safety Population	Part B
15.101.1	Shift Analysis for Hematology Laboratory Tests Abnormal Values From Baseline to Any Time During the Study by Treatment Group	Safety Population	Part A
15.101.2	Shift Analysis for Hematology Laboratory Tests Abnormal Values From Baseline to Any Time During the Study by Treatment Group	Safety Population	Part A

Summary number	Title	Population	Data Lock
15.102.1	Shift Analysis for Serum Chemistry Laboratory Tests Potentially Clinically Significant Abnormal (PCSA) Values From Baseline to Any Time During the Study by Treatment Group	Safety Population	Part A
15.102.2	Shift Analysis for Serum Chemistry Laboratory Tests Potentially Clinically Significant Abnormal (PCSA) Values From Baseline to Any Time During the Study by Treatment Group	Safety Population	Part B
15.103.1	Shift Analysis for Hematology Laboratory Tests Potentially Clinically Significant Abnormal (PCSA) Values From Baseline to Any Time During the Study by Treatment Group	Safety Population	Part A
15.103.2	Shift Analysis for Hematology Laboratory Tests Potentially Clinically Significant Abnormal (PCSA) Values From Baseline to Any Time During the Study by Treatment Group	Safety Population	Part B
15.104.1	Shift Analysis for Serum Chemistry Laboratory Tests Potentially Clinically Significant Abnormal (PCSA) Values From Normal Values at Baseline to Any Time During the Study by Treatment Group	Safety Population	Part A
15.104.2	Shift Analysis for Serum Chemistry Laboratory Tests Potentially Clinically Significant Abnormal (PCSA) Values From Normal Values at Baseline to Any Time During the Study by Treatment Group	Safety Population	Part B
15.105.1	Shift Analysis for Hematology Laboratory Tests Potentially Clinically Significant Abnormal (PCSA) Values From Normal Values at Baseline to Any Time During the Study by Treatment Group	Safety Population	Part A
15.105.2	Shift Analysis for Hematology Laboratory Tests Potentially Clinically Significant Abnormal (PCSA) Values From Normal Values at Baseline to Any Time During the Study by Treatment Group	Safety Population	Part B
15.106.1	Anemia Panel/B12 Laboratory Tests Results and Change From Baseline by Treatment Group	Safety Population	Part A
15.106.2	Anemia Panel/B12 Laboratory Tests Results and Change From Baseline by Treatment Group	Safety Population	Part B
15.107.1	Shift Analysis of CTCAE Grade For Hemoglobin From Baseline to Any Time During the Study by Treatment Group	Safety Population	Part A
15.107.2	Shift Analysis of CTCAE Grade For Hemoglobin From Baseline to Any Time During the Study by Treatment Group	Safety Population	Part B
15.108.1	Distribution of Maximal AST, ALT, and GGT Values During Study by Treatment Group	Safety Population	Part A
15.108.2	Distribution of Maximal AST, ALT, and GGT Values During Study by Treatment Group	Safety Population	Part B
15.109.1	Vital Signs Values and Changes From Baseline to Each Visit by Treatment Group	Safety Population	Part A
15.109.2	Vital Signs Values and Changes From Baseline to Each Visit by Treatment Group	Safety Population	Part B

Summary number	Title	Population	Data Lock
15.110.1	Vital Signs Potentially Clinically Significant Abnormal Values by Treatment Group	Safety Population	Part A
15.110.2	Vital Signs Potentially Clinically Significant Abnormal Values by Treatment Group	Safety Population	Part B
15.111.1	Electrocardiogram Findings Based on Investigator Interpretation at Each Visit by Treatment Group	Safety Population	Part A
15.111.2	Electrocardiogram Findings Based on Investigator Interpretation at Each Visit by Treatment Group	Safety Population	Part B
15.112.1	Electrocardiogram Findings Based on ERT Interpretation at Each Visit by Treatment Group	Safety Population	Part A
15.112.2	Electrocardiogram Findings Based on ERT Interpretation at Each Visit by Treatment Group	Safety Population	Part B
15.113.1	Electrocardiogram Findings Based on Investigator Interpretation Shifts From Baseline to Each Visit by Treatment Group	Safety Population	Part A
15.113.2	Electrocardiogram Findings Based on Investigator Interpretation Shifts From Baseline to Each Visit by Treatment Group	Safety Population	Part B
15.114.1	Electrocardiogram Findings Based on ERT Interpretation Shifts From Baseline to Each Visit by Treatment Group	Safety Population	Part A
15.114.2	Electrocardiogram Findings Based on ERT Interpretation Shifts From Baseline to Each Visit by Treatment Group	Safety Population	Part B
15.115.1	Electrocardiogram Variables Evaluated by ERT Results and Changes From Baseline to Each Visit by Treatment Group	Safety Population	Part A
15.115.2	Electrocardiogram Variables Evaluated by ERT Results and Changes From Baseline to Each Visit by Treatment Group	Safety Population	Part B
15.116.1	QTc Intervals (Bazett and Fridericia) at Baseline by Treatment Group	Safety Population	Part A
15.116.2	QTc Intervals (Bazett and Fridericia) at Baseline by Treatment Group	Safety Population	Part B
15.117.1	Shift Analysis For QTc Intervals (Bazett and Fridericia) From Baseline to Each Visit and Overall by Treatment Group	Safety Population	Part A
15.117.2	Shift Analysis For QTc Intervals (Bazett and Fridericia) From Baseline to Each Visit and Overall by Treatment Group	Safety Population	Part B
15.118.1	Concomitant Medications by Therapeutic Class, Preferred Term, and Treatment Group	Safety Population	Part A
15.118.2	Concomitant Medications by Therapeutic Class, Preferred Term, and Treatment Group	Safety Population	Part B

13.2. Individual Patient Data Listings

Listing Number	Title	Population	Data Lock
16.2.1.01.1	Patient Disposition by Treatment Group	ITT Population	Part A
16.2.1.01.2	Patient Disposition by Treatment Group	ITT Population	Part B
16.2.1.02	Patients Who Did Not Meet Screening Criteria		Part A
16.2.2.01.1	Protocol Violations by Treatment Group	ITT Population	Part A
16.2.2.01.2	Protocol Violations by Treatment Group	ITT Population	Part B
16.2.2.02	Major Protocol Violations by Treatment Group	ITT Population	Part A
16.2.4.01	Demographics by Treatment Group	ITT Population	Part A
16.2.4.02	Childbearing Potential by Treatment Group (Females Only)	ITT Population	Part A
16.2.4.03	Medical History by Treatment Group	ITT Population	Part A
16.2.4.04	PPMS History by Treatment Group	ITT Population	Part A
16.2.4.05	MS Disease Modifying Treatment History by Treatment Group	ITT Population	Part A
16.2.4.06	Chest X-Ray by Treatment Group	ITT Population	Part A
16.2.4.07	Informed Consent for Cerebrospinal Fluid and Optical Coherence Tomography by Treatment Group	ITT Population	Part A
16.2.4.08.1	Liver Disease Risk Factor Evaluation by Treatment Group	ITT Population	Part A
16.2.4.08.2	Liver Disease Risk Factor Evaluation by Treatment Group	ITT Population	Part B
16.2.4.09	Tobacco Usage by Treatment Group	ITT Population	Part A
16.2.5.01.1	Dosing by Treatment Group	ITT Population	Part A
16.2.5.01.2	Dosing by Treatment Group	ITT Population	Part B
16.2.5.02.1	Study Medication Interruption by Treatment Group	ITT Population	Part A
16.2.5.02.2	Study Medication Interruption by Treatment Group	ITT Population	Part B
16.2.5.03	Prior Drug Administration by Treatment Group	ITT Population	Part A
16.2.5.04.1	Study Drug Accountability by Treatment Group	ITT Population	Part A
16.2.5.04.2	Study Drug Accountability by Treatment Group	ITT Population	Part B
16.2.5.05.1	Pack Accountability by Treatment Group	ITT Population	Part A
16.2.5.05.2	Pack Accountability by Treatment Group	ITT Population	Part B
16.2.6.01	MRI Scan by Treatment Group	ITT Population	Part A
16.2.6.02	MRI Parameters by Treatment Group	ITT Population	Part A
16.2.6.03.1	Confirmed Disability Progression (CDP) by Treatment Group	ITT Population	Part A
16.2.6.03.2	Confirmed Disability Progression (CDP) by Treatment Group	ITT Population	Part B
16.2.6.04.1	Neurological Assessments by Treatment Group	ITT Population	Part A
16.2.6.04.2	Neurological Assessments by Treatment Group	ITT Population	Part B
16.2.6.05.1	CVLT-II by Treatment Group	ITT Population	Part A

Listing Number	Title	Population	Data Lock
16.2.6.05.2	CVLT-II by Treatment Group	ITT Population	Part B
16.2.6.06.1	BVMT-R by Treatment Group	ITT Population	Part A
16.2.6.06.2	BVMT-R by Treatment Group	ITT Population	Part B
16.2.6.07.1	T25FW by Treatment Group	ITT Population	Part A
16.2.6.07.2	T25FW by Treatment Group	ITT Population	Part B
16.2.6.08.1	9HPT by Treatment Group	ITT Population	Part A
16.2.6.08.2	9HPT by Treatment Group	ITT Population	Part B
16.2.6.09.1	SDMT by Treatment Group	ITT Population	Part A
16.2.6.09.2	SDMT by Treatment Group	ITT Population	Part B
16.2.6.10.1	LCVA by Treatment Group	ITT Population	Part A
16.2.6.10.2	LCVA by Treatment Group	ITT Population	Part B
16.2.6.11.1	MSWS-12 by Treatment Group	ITT Population	Part A
16.2.6.11.2	MSWS-12 by Treatment Group	ITT Population	Part B
16.2.6.12.1	Clinical Relapse by Treatment Group	ITT Population	Part A
16.2.6.12.2	Clinical Relapse by Treatment Group	ITT Population	Part B
16.2.7.01.1	Adverse Events by Treatment Group	ITT Population	Part A
16.2.7.01.2	Adverse Events by Treatment Group	ITT Population	Part B
16.2.7.02.1	Deaths by Treatment Group	ITT Population	Part A
16.2.7.02.2	Deaths by Treatment Group	ITT Population	Part B
16.2.7.03.1	Serious Adverse Events by Treatment Group	ITT Population	Part A
16.2.7.03.2	Serious Adverse Events by Treatment Group	ITT Population	Part B
16.2.7.04.1	Adverse Events Causing Discontinuation of Treatment by Treatment Group	ITT Population	Part A
16.2.7.04.2	Adverse Events Causing Discontinuation of Treatment by Treatment Group	ITT Population	Part B
16.2.7.05	Adverse Events in Patients Who Did Not Meet Screening Criteria		Part A
16.2.8.01	Laboratory Reference Ranges		Part A
16.2.8.02.1	Serum Chemistry Laboratory Tests Results by Treatment Group	ITT Population	Part A
16.2.8.02.2	Serum Chemistry Laboratory Tests Results by Treatment Group	ITT Population	Part B
16.2.8.03.1	Hematology Laboratory Tests Results by Treatment Group	ITT Population	Part A
16.2.8.03.2	Hematology Laboratory Tests Results by Treatment Group	ITT Population	Part B
16.2.8.04.1	Coagulation Laboratory Test Results by Treatment Group	ITT Population	Part A
16.2.8.04.2	Coagulation Laboratory Test Results by Treatment Group	ITT Population	Part B
16.2.8.05	Urinalysis Laboratory Tests Results by Treatment Group	ITT Population	Part A

Listing Number	Title	Population	Data Lock
16.2.8.06.1	Pregnancy Test Results by Treatment Group (Females Only)	ITT Population	Part A
16.2.8.06.2	Pregnancy Test Results by Treatment Group (Females Only)	ITT Population	Part B
16.2.8.07.1	Serology Tests Results by Treatment Group	ITT Population	Part A
16.2.8.07.2	Serology Tests Results by Treatment Group	ITT Population	Part B
16.2.8.08.1	Anemia Panel Tests Results by Treatment Group	ITT Population	Part A
16.2.8.08.2	Anemia Panel Tests Results by Treatment Group	ITT Population	Part B
16.2.8.09.1	Serum Chemistry Laboratory Tests Potentially Clinically Significant Abnormal Results by Treatment Group	ITT Population	Part A
16.2.8.09.2	Serum Chemistry Laboratory Tests Potentially Clinically Significant Abnormal Results by Treatment Group	ITT Population	Part B
16.2.8.10.1	Hematology Laboratory Tests Potentially Clinically Significant Abnormal Results by Treatment Group	ITT Population	Part A
16.2.8.10.2	Hematology Laboratory Tests Potentially Clinically Significant Abnormal Results by Treatment Group	ITT Population	Part B
16.2.8.11.1	Treatment Schedule	ITT Population	Part A
16.2.8.11.2	Treatment Schedule	ITT Population	Part B
16.2.8.12.1	Vital Signs Values by Treatment Group	ITT Population	Part A
16.2.8.12.2	Vital Signs Values by Treatment Group	ITT Population	Part B
16.2.8.13.1	Vital Signs Potentially Clinically Significant Abnormal Values by Treatment Group	ITT Population	Part A
16.2.8.13.2	Vital Signs Potentially Clinically Significant Abnormal Values by Treatment Group	ITT Population	Part B
16.2.8.14.1	Electrocardiogram Findings by Treatment Group	ITT Population	Part A
16.2.8.14.2	Electrocardiogram Findings by Treatment Group	ITT Population	Part B
16.2.8.15.1	Electrocardiogram Variable Results by Treatment Group	ITT Population	Part A
16.2.8.15.2	Electrocardiogram Variable Results by Treatment Group	ITT Population	Part B
16.2.8.16.1	Physical Examination Not Done Records by Treatment Group	ITT Population	Part A
16.2.8.16.2	Physical Examination Not Done Records by Treatment Group	ITT Population	Part B
16.2.8.17.1	Prior and Concomitant Medications by Treatment Group	ITT Population	Part A
16.2.8.17.2	Prior and Concomitant Medications by Treatment Group	ITT Population	Part B
16.2.8.18	Pharmacokinetic Sampling Times by Treatment Group	ITT Population	Part A
16.2.8.19.1	Optical Coherence Tomography by Treatment Group	ITT Population	Part A
16.2.8.19.2	Optical Coherence Tomography by Treatment Group	ITT Population	Part B
16.2.8.20.1	Reasons for Unscheduled Visit by Treatment Group	ITT Population	Part A
16.2.8.20.2	Reasons for Unscheduled Visit by Treatment Group	ITT Population	Part B
16.2.8.21.1	Liver or Biliary Tract Ultrasound by Treatment Group	ITT Population	Part A

Listing Number	Title	Population	Data Lock
16.2.8.21.2	Liver or Biliary Tract Ultrasound by Treatment Group	ITT Population	Part B
16.2.8.22.1	Other Diagnostics by Treatment Group	ITT Population	Part A
16.2.8.22.2	Other Diagnostics by Treatment Group	ITT Population	Part B

13.3. Graphs

Graph Number	Title	Population	Data Lock
17.1	Adjusted Means Percentage Brain Volume Change (PBVC) from Baseline to Each Visit.	mITT1 Population	Part A
17.2	Adjusted Mean Percentage Brain Volume Change (PBVC) from Baseline to Each Visit.	PP Population	Part A
17.3.1	Kaplan-Meier Curves for Time to 12 Weeks Confirmed Disability Progression as Measured by EDSS by Treatment Group	ITT Population	Part A
17.3.2	Kaplan-Meier Curves for Time to 12 Weeks Confirmed Disability Progression as Measured by EDSS by Treatment Group	ITT Population	Part B
17.4.1	Kaplan-Meier Curves for Time to 12 Weeks Confirmed Disability Progression as Measured by EDSS and T25FW by Treatment Group	ITT Population	Part A
17.4.2	Kaplan-Meier Curves for Time to 12 Weeks Confirmed Disability Progression as Measured by EDSS and T25FW by Treatment Group	ITT Population	Part B
17.5.1	Means Timed 25-Foot Walk Score Change from Baseline to Each Visit	mITT2 Population	Part A
17.5.2	Means Timed 25-Foot Walk Score Change from Baseline to Each Visit	mITT2 Population	Part B
17.6.1	Kaplan-Meier Curves for Time to 12 Weeks Confirmed Disability Progression as Measured by at least 1 of 4 Types of Events by Treatment Group	ITT Population	Part A
17.6.2	Kaplan-Meier Curves for Time to 12 Weeks Confirmed Disability Progression as Measured by at least 1 of 4 Types of Events by Treatment Group	ITT Population	Part B
17.7.1	Kaplan-Meier Curves for Time to 24 Weeks Confirmed Disability Progression as Measured by EDSS by Treatment Group	ITT Population	Part A
17.7.2	Kaplan-Meier Curves for Time to 24 Weeks Confirmed Disability Progression as Measured by EDSS by Treatment Group	ITT Population	Part B
17.8.1	Means 9-Hole Peg Test Score Change from Baseline to Each Visit	mITT2 Population	Part A
17.8.2	Means 9-Hole Peg Test Score Change from Baseline to Each Visit	mITT2 Population	Part B
17.9.1	Adjusted Means Symbol Digit Modalities Test Score Change from Baseline to Each Visit	mITT2 Population	Part A
17.9.2	Adjusted Means Symbol Digit Modalities Test Score Change from Baseline to Each Visit	mITT2 Population	Part B
17.10.1	Adjusted Means for Low Contrast Visual Acuity Score (Chart Type 100%) Change from Baseline to Each Visit	mITT2 Population	Part A

Graph Number	Title	Population	Data Lock
17.10.2	Adjusted Means for Low Contrast Visual Acuity Score (Chart Type 100%) Change from Baseline to Each Visit	mITT2 Population	Part B
17.11.1	Adjusted Means for Low Contrast Visual Acuity Score (Chart Type 2.5%) Change from Baseline to Each Visit	mITT2 Population	Part A
17.11.2	Adjusted Means for Low Contrast Visual Acuity Score (Chart Type 2.5%) Change from Baseline to Each Visit	mITT2 Population	Part B
17.12.1	Adjusted Means for Low Contrast Visual Acuity Score (Chart Type 1.25%) Change from Baseline to Each Visit	mITT2 Population	Part A
17.12.2	Adjusted Means for Low Contrast Visual Acuity Score (Chart Type 1.25%) Change from Baseline to Each Visit	mITT2 Population	Part B
17.13.1	Adjusted Means 12-Item Multiple Sclerosis Walking Scale Score Change from Baseline to Each Visit	mITT2 Population	Part A
17.13.2	Adjusted Means 12-Item Multiple Sclerosis Walking Scale Score Change from Baseline to Each Visit	mITT2 Population	Part B
17.14.1	Kaplan-Meier Curves for Time to 12 Weeks Confirmed Disability Progression as Measured by T25FW by Treatment Group	ITT Population	Part A
17.14.2	Kaplan-Meier Curves for Time to 12 Weeks Confirmed Disability Progression as Measured by T25FW by Treatment Group	ITT Population	Part B
17.15.1	Kaplan-Meier Curves for Time to Early Termination	ITT Population	Part A
17.15.2	Kaplan-Meier Curves for Time to Early Termination	ITT Population	Part B
17.16.1	Kaplan-Meier Curves for Time to Early Termination Due to Adverse Events	ITT Population	Part A
17.16.2	Kaplan-Meier Curves for Time to Early Termination Due to Adverse Events	ITT Population	Part B
17.17.1	Box Plots for Hematology Laboratory Tests Results Over Time by Treatment Group	Safety Population	Part A
17.17.2	Box Plots for Hematology Laboratory Tests Results Over Time by Treatment Group	Safety Population	Part B
17.18.1	Box Plots for Fibrinogen, CRP, and P-Amylase Laboratory Test Results Over Time by Treatment Group	Safety Population	Part A
17.18.2	Box Plots for Fibrinogen, CRP, and P-Amylase Laboratory Test Results Over Time by Treatment Group	Safety Population	Part B
17.19.1	Evaluation of Drug-Induced Serious Hepatotoxicity (eDISH) by Treatment Group	Safety Population	Part A
17.19.2	Evaluation of Drug-Induced Serious Hepatotoxicity (eDISH) by Treatment Group	Safety Population	Part B

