#### **4.3.1. Patient Withdrawal Criteria**

A patient may withdraw or be withdrawn from the study for the following reasons:

- death
- patient withdrew consent
- sponsor requested patient to be withdrawn
- study terminated by the sponsor
- protocol violation
- non-compliance with study drug
- lost to follow-up/failure to return
- adverse event
- lack of efficacy (according to the investigators decision)
- pregnancy

For patients in the 1.5 mg arm who were withdrawn from study treatment, the reason will be recorded as ‘sponsor requested patient to be withdrawn’.

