### **9.8. Safety Variables and Analysis**

#### **9.8.1. Safety Variables**

All safety analysis will be performed for ST population. Summaries will be presented by treatment group and for all patients unless otherwise noted.

The overall safety and tolerability of laquinimod treatment will be assessed throughout the study by evaluating adverse events and the following additional safety variables:

- clinical laboratory tests
- vital signs
- 12-lead ECG
- concomitant medications use throughout the study

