3.2.6. Tolerability Variables and Endpoints

- Proportion of patients (%) who prematurely discontinue treatment, reasons for discontinuation, and time to early termination (ET).
- Proportion of patients (%) who prematurely discontinue treatment due to adverse events, and time to ET due to adverse events.

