7.6. Tolerability Variables and Analysis

Tolerability analysis will be performed only for placebo and laquinimod 0.6 mg patients and will be presented by proportion of patients (%) who prematurely discontinued treatment and reason of discontinuation (including early termination due to AEs). Additionally the time to Early Termination (ET) and time to ET due to AEs will be presented by Kaplan-Meier curves. No statistical inference will be done.

All analyses presented in the section will be repeated to include both part A and part B when the study is completed.

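### The Kaplan-Meier display of time to stopping for adverse events has no censoring rule, and under the usual convention it slightly overstates the probability of stopping for that reason

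*SAP*

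**What the plan says.** SAP Section 3.2.6 names as a tolerability endpoint the "Proportion of patients (%) who prematurely discontinue treatment due to adverse events, and time to ET due to adverse events". Section 7.6 says that "time to ET due to AEs will be presented by Kaplan-Meier curves", alongside a curve for early termination (ET) for any reason. Section 13.3 lists "Kaplan-Meier Curves for Time to Early Termination Due to Adverse Events" as Graphs 17.16.1 (Part A) and 17.16.2 (Part B), both in the ITT population.

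Three limits are stated in Section 7.6:

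- "Tolerability analysis will be performed only for placebo and laquinimod 0.6 mg patients".
- The proportion who stopped early is reported with the reason, adverse events included (Tables 15.80.1 and 15.80.2).
- "No statistical inference will be done".

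No event or censoring rule for the adverse-event curve appears anywhere. The detailed rules in SAP Section 7.4.1 concern confirmed disability progression. Protocol Section 3.6.7 defines ET as stopping study drug. Protocol Section 4.3.1 lists many reasons besides adverse events, among them withdrawn consent, loss to follow-up, pregnancy, lack of efficacy and death.

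**The concern.** ET due to an adverse event is one of several mutually exclusive ways to stop drug. Once a patient has stopped for another reason, this event cannot occur. Ordinary Kaplan-Meier practice would censor that patient, which treats the patient as still at risk of stopping for an adverse event. One minus Kaplan-Meier then describes a setting in which nobody stops for any other reason. It can never lie below the cumulative incidence that patients actually experience.

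The protocol also gives some reason to doubt that such censoring would be uninformative. Under Section 7.1.7, when an adverse event is not itself severe enough to warrant stopping but needs a prohibited drug, the recorded reason is the prohibited medication. Some other-reason stops are therefore linked to adverse events.

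What is at stake is how a reader interprets one descriptive curve for a stated tolerability endpoint, mainly at its long end in the Part B version.

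**Working it through.** **The plan's own figure.** The only discontinuation rate in the documents is the 10% dropout in the sample size (Protocol Section 9.2). That calculation reproduces. With 126 per arm, a difference of 0.3 and a standard deviation of 0.8, the standardised distance is 0.3 / (0.8 × √(2/126)) = 2.98. Two-sided 5% power is then Φ(2.98 − 1.96) = 84.5%, against 84% stated. Also 252 / 0.9 = 280, and 280 + 95 = 375. This bears on the point only by supplying the 10%. The documents give no expected rate of stopping for adverse events.

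**Inputs**

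- d, the share who stop drug for any reason by week 48: 0.10, from the plan. Reading that dropout as drug stops by week 48 is an assumption. A value of 0.15 is a further assumption.
- f, the share of stops due to adverse events: 0.3 to 0.5, assumed.
- Hazards constant over time, assumed.
- Times: week 48, the minimum length of Part A; and week 120, beyond which few patients are expected to need visits (SAP Table 2, footnote d).

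**Formulas.** Total weekly hazard h = −ln(1 − d)/48. At week w:

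- cumulative incidence of ET due to adverse events = f × (1 − e^(−hw));
- one minus Kaplan-Meier with other-reason stops censored = 1 − e^(−fhw).

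For d = 0.10, h = 0.002195, and the share still on drug is 0.900 at week 48 and 0.9^2.5 = 0.7684 at week 120. For d = 0.15, h = 0.003386, and the share still on drug at week 120 is 0.85^2.5 = 0.6661.

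| d | f | Week | Cumulative incidence | 1 − Kaplan-Meier | Excess (points) |
|---|---|---|---|---|---|
| 0.10 | 0.3 | 48 | 3.00% | 3.11% | 0.11 |
| 0.10 | 0.5 | 48 | 5.00% | 5.13% | 0.13 |
| 0.10 | 0.3 | 120 | 6.95% | 7.60% | 0.65 |
| 0.10 | 0.5 | 120 | 11.58% | 12.34% | 0.76 |
| 0.15 | 0.3 | 120 | 10.02% | 11.48% | 1.46 |
| 0.15 | 0.5 | 120 | 16.69% | 18.38% | 1.69 |

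With half of stops due to adverse events, higher assumed rates give larger excesses at week 120: 3.0 points if 20% stop by week 48, and 6.5 points if 30% do.

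**What the crude proportion would show.** Take d = 0.10 and f = 0.5, and let follow-up end uniformly between weeks 48 and 120 (assumed). The mean share still on drug at the end of follow-up is (0.900 − 0.7684)/(0.002195 × 72) = 0.833. The crude share stopping for an adverse event is therefore 0.5 × (1 − 0.833) = 8.4%. That is about 3.2 points below the week-120 cumulative incidence of 11.6%, whereas Kaplan-Meier is only 0.76 point above it. Unequal follow-up accounts for most of any gap between the table and either curve.

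**The case against.** The strongest reply is that nothing rests on this curve. It is descriptive, no test is attached, the SAP does not say that one minus Kaplan-Meier will be read as an incidence, and the observed proportions by reason are tabulated. On the plan's own dropout the excess at week 120 is about one patient of the 140 per arm (0.0076 × 140 = 1.1). The standard error of an 11.6% proportion in 140 patients is √(0.116 × 0.884/140) = 2.7 points, so the excess is under a third of one standard error. All of this stands and sets the weight of the point. It does not make Kaplan-Meier the better display. The tabulated proportions ignore variable follow-up, the Kaplan-Meier curve under the usual convention ignores competing reasons, and neither gives the probability of stopping for an adverse event by a given week.

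A reader might infer more than the documents support:

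- *That the SAP censors other-reason stops.* It states no rule. The convention is likely but inferred, and the firm gap is the missing rule.
- *That Tables 15.80 give the true cumulative proportion, so that disagreement with the curve proves bias.* They give crude proportions over unequal follow-up, which a cumulative-incidence curve would not match either.
- *That the comparison between arms is distorted.* This would need other-reason stops to differ by arm, and the documents say nothing on that.
- *That the sponsor's stopping of the 1.5 mg arm competes here.* That arm is outside the tolerability analysis.
- *That the ITT population is an error.* Protocol Section 9.8.1 says "All safety analysis will be performed for ST population" and covers tolerability in the same section. SAP Section 6.2 foresees ITT patients who were never treated, and Section 5.6 starts study days at the first dose, so such patients have no start time for this curve. But the SAP's preface says the SAP prevails over the protocol. Tables 15.80 and Graphs 17.15 and 17.16 all use ITT consistently. The first dose is given at the baseline visit after randomization, so never-dosed patients should be few. No size can be attached to this.

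**Conclusion.** The point holds as a minor one. The plan shows a cause-specific event by Kaplan-Meier without saying how other reasons for stopping are handled. If those patients are censored, the direction of the error is certain: one minus Kaplan-Meier is too high. Its size is small on the plan's own dropout: about 0.1 percentage point at week 48 and 0.65 to 0.76 point at week 120. It reaches 1.5 to 1.7 points at week 120 only if 15% rather than 10% stop by week 48. These figures rest on constant hazards, on 30% to 50% of stops being due to adverse events, and on reading the 10% dropout as drug stops by week 48. No efficacy or safety conclusion depends on the curve.

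**What to change.** In SAP Section 7.6 and Graphs 17.16.1 and 17.16.2:

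- Plot the cumulative incidence (Aalen-Johansen) of ET due to adverse events by treatment group, with ET for any other reason and death as competing events.
- State that only patients still on treatment at the data lock are censored (for the Part B display, those who complete on treatment).
- Keep Kaplan-Meier for ET for any reason (Graphs 17.15.1 and 17.15.2), where stops for different reasons do not compete.
- Use one population for Tables 15.80 and Graphs 17.15 and 17.16. If the safety population is chosen, change all three; moving only 17.16 would give the outputs different denominators.

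The cost is a few lines of SAP text and minor reprogramming of one descriptive figure. Reasons for early termination are already collected (Protocol Sections 3.11.4 and 4.3), so no new data are needed.
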